2.6.4 Concomitant treatments

During the study period, all the participants in the COPD group will maintain their previous treatment regimen. If additional medications or other treatments are used during the study period due to any reasons, the details (e.g. the name, administration time and dosage of the medication) should be documented.

Besides, participants in the healthy control group and healthy intervention group should not take any medications during the full study period. If drugs or other treatments are adopted due to sudden diseases, relevant information should be documented and researchers will evaluate whether they should be withdrawn from the study.

3. Outcome measurement

Primary outcomes will be blood flow curve and blood perfusion units (PU) of relevant sites along the Heart and Lung meridians.

4. Safety evaluation

Adverse events (AEs) that occur during the trial will be recorded and assessed by the investigators during each examination session and at each visit next time. If serious AEs occur, the researchers should report them to the principal investigator and ethics committee immediately, who will make a decision on whether the participant should be withdrawn from the study.

5. Ethical approval and study registration

Ethics approval (approval document No: ZCMU-KY-2019-042, April 29, 2019) was obtained from the Ethics Committee of Zhejiang Chinese Medical University. The purpose, contents and potential risks of the research will be fully explained to the

participants and their families. All participants will complete the informed consent form before participating in the study. All participants' personal and disease information will be kept confidential.

6. Quality control

(1) The trial protocol has been modified according to suggestions from experienced acupuncturists.

(2) Before the trial, all researchers who enroll participants and collect data must attend a series of training sessions. These training sessions will ensure that all research staff involved fully understand the trial protocol and standard operating procedures (SOP).

[figure not shown]
(3) SOP of the examination method is designed before the trial.

(4) Data collection will be performed in accordance with the pre-approved protocols. All assessors will be trained uniformly to record outcomes and fill in the case report forms. One independent supervisor will regularly verify the consistency of the raw data and the recorded data. Data management and monitoring will also be performed by using ResMan Research Manager (<http://www.medresman.org>).

(5) During the trial, clinical supervisors will guide and supervise the operators regularly (once every three months).

(6) Economic compensation is adopted to improve compliance and reduce dropouts and withdrawals of participants.

7. Flow diagram of the study design

Part3. Statistical Analysis Plan

1. Data entry and storage

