ID: 2019ZY004-MERIDIAN

Research title:

A study on the microcirculatory characteristics of meridian phenomenon for the heart and lung meridians based on patients with chronic obstructive pulmonary disease

Date: March 25, 2019

Study Protocol

Part1. Study introduction and objectives

(1) Brief introduction

This study will include 40 patients with chronic obstructive pulmonary disease (COPD), and 80 healthy volunteers. Laser doppler examination will be adopted to assess the microcirculatory characteristics of meridian phenomena and investigate the site specificity for the meridian-visceral association and surface-surface association between two specific meridians.

(2) Study objects

1) This study aims to detect the microcirculatory characteristics of meridian phenomena using laser doppler flowmetry(LDF). Thus, the biological characteristics of meridian phenomenon could be presented objectively in a scientific methodology.

2) This study aims to investigate the site specificity for the meridian-visceral association and surface-surface association between two specific meridians.

Part2. Study program

1.Study subjects

The subjects of this study include two kinds of participants, which includes healthy volunteers and patients with COPD.

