2.6.3 Procedures for LDF examination and moxibustion intervention

A four-channel LDF (PeriFlux System 5000, Sweden) will be used to measure the microcirculatory characteristics of meridian phenomena for the Heart and Lung meridians, which could monitor 4 measuring sites simultaneously. The participants will be asked to stabilize for 15 minutes in a supine position in the experimental room before formal examination. They will be informed to keep silent and normal breath and avoid limb movement during the whole measuring period. The probes will be left at relevant measuring sites. Blood flow curve will be recorded constantly using Perisoft software (PeriFlux, Sweden). Perfusion units (PU) of microcirculatory flux in the measuring sites will be calculated by the software [PU = concentration of moving blood cells (CMBC) × velocity (V)].

(1) Healthy control group and COPD group

The probes will be left at 4 measuring acupoints, which include Shenmen (HT7) and Shaohai (HT3) of the Heart meridian, Taiyuan (LU9) and Chize (LU5) of the Lung meridian. The blood flow curve and PU will be recorded for 5 minutes.

(2) Healthy intervention group

Two sessions of moxibustion intervention will be performed in the Heart meridian and Lung meridian successively. The washout period between the two sessions is at least one day.

1) Intervention in the Heart meridian: By igniting the moxa stick and inserting it into a homemade moxibustion holder to adjust the appropriate angle and height, moxibustion will be performed above Shaohai (HT3) of Heart meridian for 15 minutes. During moxibustion, the probes will detect the blood flow curve and PU in four sites in two meridians, which include Shaohai (HT3) of the Heart meridian, the midpoint of the Heart meridian along the left forearm (i.e. the midpoint of the line

between HT3 and HT7), Chize (LU5) of the Lung meridian, and the midpoint of the Lung meridian along the left forearm(i.e. the midpoint of the line between LU5 and LU9). The measuring time points include 5 minutes before moxibustion, 15 minutes during moxibustion and 5 minutes after stopping moxibustion.

2)Intervention in the Lung meridian: The moxibustion acupoint is Chize (LU5) of the Lung meridian. The LDF examination, moxibustion procedure, measuring sites and time points are the same as 1).

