2.3 Statistical analysis

All data in this study will be analyzed by a blinded statistician. Independent sample T test and Chi-square test (χ^2 test) will be used for numerical variables and categorical variables, respectively. When the distribution of variables is abnormal, a non-parametric test will be selected. A P value < 0.05 will be considered statistically significance.

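### PU is primary at every measured site with no primary site or contrast, no multiplicity rule and no direct Lung-versus-Heart test for the site-specificity objective

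*Combined protocol and SAP*

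**What the plan says.** Part 1, (2) sets two objectives. The first is to describe microcirculation along the meridians by laser Doppler. The second reads: "This study aims to investigate the site specificity for the meridian-visceral association and surface-surface association between two specific meridians".

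Part 2, section 3 gives the outcome: "Primary outcomes will be blood flow curve and blood perfusion units (PU) of relevant sites along the Heart and Lung meridians". It ranks no site and does not say how a recording becomes a number.

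Section 2.6.3 names the sites. For the healthy control and COPD groups, "The probes will be left at 4 measuring acupoints": HT7 and HT3 on the Heart meridian, LU9 and LU5 on the Lung meridian. For these groups, "The blood flow curve and PU will be recorded for 5 minutes". The healthy intervention group has two sessions. Each records HT3, LU5 and the two forearm midpoints for 5 minutes before, 15 minutes during and 5 minutes after moxibustion.

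SAP 2.3 is the whole inferential plan. It names "Independent sample T test and Chi-square test" for numerical and categorical variables respectively, and adds: "When the distribution of variables is abnormal, a non-parametric test will be selected". The threshold is: "A P value < 0.05 will be considered statistically significance". It assigns no test to any comparison and includes no paired test, interaction or multiplicity rule.

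**The concern.** Three things follow.

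- **Multiplicity.** With four co-equal primary acupoints and one unadjusted threshold, a significant result at any of them can be reported as the primary finding.
- **Specificity.** Objective 2 concerns a difference between Lung and Heart sites in the same person. Without a test of that difference, the evidence left is a list of separate site-level P values. Significance at one site and not at another does not show that the sites differ.
- **Paired data.** The before, during and after recordings in the intervention group are within-person. An independent-sample test on single-site values does not fit them.

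All four probes record at once on each participant, so the data for a direct comparison will exist. What is missing is the statement of what will be compared.

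**Working it through.** **Inputs from the documents.** 40 per group (2.1, 2.4); 4 acupoints in COPD and control (2.6.3); alpha 0.05 (SAP 2.3). The total of 120 has no effect size, SD or power behind it (2.2), so only the sum 40 + 80 = 120 can be checked.

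**Assumptions.** Two-sided tests, normal data, equal correlation ρ between all sites (0 / 0.5 / 0.9), and shifts in units of the site SD. The documents give no correlation, mean or SD for PU.

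**1. At least one false positive over 4 acupoints.** At ρ = 0: 1 − 0.95⁴ = 0.185. For ρ > 0, integrate over the shared normal component u: 1 − ∫ φ(u) [Φ((1.96 − √ρ·u)/√(1−ρ)) − Φ((−1.96 − √ρ·u)/√(1−ρ))]⁴ du. This gives 0.156 at ρ = 0.5 and 0.094 at ρ = 0.9. Simulated t tests agree (0.188 / 0.156 / 0.094). With Holm over the four sites: 0.050 / 0.043 / 0.026.

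**2. Specificity inferred from separate tests.** Suppose COPD shifts all four sites equally, so there is no specificity, and the pattern read as Lung-specific is at least one Lung site and no Heart site significant. At 0.45 SD the expected test statistic is 0.45 × √(40/2) = 2.01, close to the critical value, so each site is significant in roughly half of studies and discordance is common. Simulated rates of the pattern (100,000 runs):

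| Equal shift | ρ = 0 | ρ = 0.5 | ρ = 0.9 |
|---|---|---|---|
| 0.3 SD | 25.0% | 14.6% | 5.6% |
| 0.45 SD | 18.3% | 13.3% | 6.0% |
| 0.6 SD | 5.5% | 6.8% | 4.1% |
| 0.8 SD | 0.3% | 1.2% | 1.2% |

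Requiring both Lung sites and no Heart site at 0.45 SD gives 6.3% / 3.3% / 1.3%.

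**3. A direct contrast.** Take the mean of the two Lung sites minus the mean of the two Heart sites per person. With equal site SDs its variance is (1+ρ)/2 + (1+ρ)/2 − 2ρ = 1 − ρ, and an equal shift cancels. The error is then 5% two-sided, 2.5% favouring Lung.

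This depends on scale. On raw PU with Lung SDs 1.5 times Heart SDs (assumed) and an equal 0.45 SD shift, the contrast moves by 1.5 × 0.45 − 0.45 = 0.225. Its variance is (1.5² + 1)(1+ρ)/2 − 2 × 1.5ρ = 1.625 − 1.375ρ. The standardised shift is 0.225/√(1.625 − 1.375ρ) = 0.177 / 0.232 / 0.361, and with 40 per group false Lung specificity is about 12% / 18% / 36%.

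**4. Power cost.** A single site has 80% power for 0.634 SD at alpha 0.05, and 61% at Holm's first step (0.05/4 = 0.0125). If only one Lung site shifts by 0.634 SD, the contrast moves by 0.634/2 = 0.317. The standardised effect is 0.317/√(1−ρ) = 0.317 / 0.448 / 1.002, and power is 29% / 51% / 99%. If both Lung sites shift by 0.634 SD, power is 80% / 98% / over 99%.

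**5. Intervention group.** 4 sites × 2 sessions × 2 changes from baseline = 16 possible within-person contrasts, none named as primary. These are not included in step 1.

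**The case against.** The best reply is that the study is exploratory. Its objectives are to detect and investigate, its sample size is not built on a hypothesis, and reporting four sites with confidence intervals would be proportionate. Some of this stands: the intervals are the right presentation for objective 1. But the plan labels the outcomes primary and sets a significance threshold, and the missing contrast for objective 2 matters even if multiplicity is set aside. SAP 1.1 has managers check that the methods are appropriate, which does not replace prespecification. Section 2.5 keeps the statisticians blind to the protocol, so they depend on a SAP that does not tell them what to compare.

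A second reply is that the independent-sample test is right for COPD versus control. That is so, and the contrast proposed here uses it. The misfit is confined to within-person comparisons.

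A third is that a Lung-minus-Heart difference is no safe cure. On raw PU that is correct (step 3). The sites differ anatomically, two at the wrist and two at the elbow, and the documents do not show that their SDs are equal. Logging only when data look skewed would not settle it; the scale must be fixed in advance.

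Two stronger readings do not hold. A reader might infer that the plan names no sites: section 2.6.3 names all of them, and what is absent is a ranking. A reader might also infer that the plan will treat a significant Lung site beside non-significant Heart sites as specificity: no section says so, and the rates in step 2 apply only if it were read that way.

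**Conclusion.** The concern holds. As written, the plan allows four unadjusted co-equal primary tests of COPD against control, with a chance of at least one false positive of about 18.5% / 16% / 9% at assumed correlations 0 / 0.5 / 0.9, above 5% throughout. It provides no direct test of objective 2 and no test suited to the paired intervention data. These gaps are plain from the text and need no assumption.

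The size of the false-specificity risk is less certain. It is 18% / 13% / 6% for an equal 0.45 SD shift, and runs from 25% to about 1% or less over shifts of 0.3 to 0.8 SD. It should be cited as an illustration of why separate tests cannot answer the question, not as this trial's error rate. Nor should a direct contrast be credited with a 2.5% error favouring Lung without the condition that an equal effect is equal on the chosen scale.

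**What to change.** Amend Part 2, section 3 and SAP 2.3 as follows.

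- **Summary and scale.** PU is the mean over each recording window, log-transformed at each site before any subtraction. This is a fixed rule, so specificity means a difference in proportional change.
- **Meridian-visceral contrast (primary).** COPD versus healthy control on mean log PU of LU5 and LU9 minus mean log PU of HT3 and HT7, by independent-sample t test.
- **Surface-surface contrast (primary, healthy intervention group).** During-minus-before change in log PU at the treated-meridian midpoint minus that at the untreated-meridian midpoint, averaged over the two sessions, by one-sample (paired) t test. Report each session separately as well. The documents do not define this association, so the sponsor should confirm that the contrast expresses it.
- **Site-level results.** Report each of the four acupoints with a confidence interval; use Holm across the four for any significance claim. Treat the blood flow curve as descriptive.

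**Costs.** No new participants or measurements. A proportional effect equal at all four sites cancels in the first contrast and appears only in the site-level results. Power for a one-Lung-site effect of 0.634 SD is 29% / 51% / 99%, assuming equal SDs on the log scale, against 80% for a single-site test. Holm lowers single-site power for that effect to about 61%. Averaging sessions can hide an effect present in one meridian only, hence the separate reporting. The two primary contrasts use separate cohorts and answer separate questions; each tested at 0.05, they carry a joint false-positive chance of 1 − 0.95² = 9.75%, which the SAP should accept openly or control with Holm.

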1.1 Data entry

(1) The original data collection

All observation scales will be measured on a "one to one" basis according to the unified standard, and the subject will be completed independently under the guidance of the investigators to ensure complete and correct completion. In the spot, check whether the filling quantity is accurate. If any omission or blurring is found in the case report forms, the assessors should verify the original data in time.

(2) Data entry and statistics

The Excel spreadsheet is used to record the original data and ensure it is accurate and reliable. A blinded statistician is employed to carry out the statistical analysis and the research managers should verify whether the statistical methods are appropriate.

1.2 Data storage

(1) The special person is responsible for the management of various documents, and there are special folders for storage in dedicated files, so that the test researcher can view it, and have access and access records.

(2) The test documents shall be protected strictly in accordance with the confidential management principles.

(3) Test file is available for test researchers and relevant researchers view, and other irrelevant personnel should not be entitled to refer to.

(4) The equipment of storing test files has safety measures such as insect repellent, fire prevention, moisture-proof and anti-theft.

2. Statistical processing

2.1 Statistical software

SPSS v20.0 (SPSS, Chicago, IL, USA).

2.2 Data description

Measurement data is described as mean standard±deviation, median, maximum, minimum and quartile, and counting data is presented as percentage (%).

2.3 Statistical analysis

All data in this study will be analyzed by a blinded statistician. Independent sample T test and Chi-square test (χ^2 test) will be used for numerical variables and categorical variables, respectively. When the distribution of variables is abnormal, a non-parametric test will be selected. A P value < 0.05 will be considered statistically significance.

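### The SAP's only named test for numerical variables is unpaired, but the moxibustion contrasts and the site-to-site contrasts are within person

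*Combined protocol and SAP*

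**What the plan says.** Part 3, 2.3 is the whole inferential plan. It assigns "Independent sample T test and Chi-square test" to numerical and categorical variables respectively, and adds: "When the distribution of variables is abnormal, a non-parametric test will be selected". That fallback is not named, and non-normality triggers it, not pairing. No paired test, signed-rank test, repeated-measures ANOVA or mixed model appears anywhere in the documents. The SAP lists no contrasts.

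Part 2, section 3 makes PU a primary outcome. Section 2.6.3 sets how it is measured:

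- The flowmeter is one "which could monitor 4 measuring sites simultaneously".
- COPD and healthy control participants: "The probes will be left at 4 measuring acupoints" (HT7, HT3, LU9, LU5), for one 5-minute recording.
- Healthy intervention group: four sites (HT3, LU5 and the two forearm midpoints). "The measuring time points include 5 minutes before moxibustion, 15 minutes during moxibustion and 5 minutes after stopping moxibustion".
- The same group again: "Two sessions of moxibustion intervention will be performed in the Heart meridian and Lung meridian successively". For the second session, "The LDF examination, moxibustion procedure, measuring sites and time points are the same as 1".
- "Blood flow curve will be recorded constantly using Perisoft software", but the section does not say how the curve becomes one PU value per period.

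Two other sections bear on this. Part 2, 2.5 has the analysis done by statisticians blinded to the protocol. Part 3, 1.1 asks research managers to check that the methods are appropriate, but names no method.

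**The concern.** The second study objective in Part 1 concerns site specificity and the association between the two meridians. In the intervention group, three kinds of contrast bear on it: during or after versus before, treated versus untreated meridian, and Heart versus Lung session. Each compares a person with himself or herself. So does any Heart-versus-Lung site contrast within the COPD or control group.

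An independent-sample t test ignores the covariance between two readings on one person. If the correlation is positive, its standard error is too large and real effects can be missed. If it is negative, the standard error is too small. The healthy control group cannot stand in as a comparator for moxibustion: it has a single 5-minute recording and shares only HT3 and LU5 with the intervention sites. A statistician kept from the protocol would also not see the section that shows which readings belong to the same person.

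**Working it through.** **Inputs from the documents.** 40 people per group (Part 2, 2.1; 3 × 40 = 120, which agrees with 2.2). P < 0.05 (Part 3, 2.3); two-sided is assumed, because sidedness is not stated. The plan gives no power, effect size, SD or correlation, so it has no figure of its own to reproduce.

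**Assumptions.** Two normal readings per person, within-person correlation ρ, and true change d in SD units.

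**Step 1: standard error.** With equal SDs σ, the variance of the mean difference is 2σ²(1−ρ)/n. The independent-sample test uses 2σ²/n. The ratio of its SE to the correct SE is 1/√(1−ρ):

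- ρ = 0.3: 1/√0.7 = 1.20
- ρ = 0.5: 1/√0.5 = 1.41
- ρ = 0.7: 1/√0.3 = 1.83
- ρ = 0: 1.00
- ρ = −0.3: 1/√1.3 = 0.88

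**Step 2: type I error at nominal 5%** (simulated; independent t with 78 df). 2.0%, 0.65% and 0.06% at ρ = 0.3, 0.5 and 0.7; about 5% at ρ = 0; 8.5% at ρ = −0.3. The paired t test (39 df) stays at about 5% throughout.

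**Step 3: power.** For the paired test the noncentrality is d√n/√(2(1−ρ)). At d = 0.4 and n = 40 the numerator is 2.530. Dividing by 1.183, 1.000 and 0.775 gives 2.14, 2.53 and 3.27, so the noncentral t power is 55.0%, 69.4% and 89.0%. Simulation agrees.

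| True change | Independent t, ρ = 0.3 / 0.5 / 0.7 | Paired t, ρ = 0.3 / 0.5 / 0.7 |
|---|---|---|
| 0.2 SD | 10 / 7 / 3% | 18 / 23 / 36% |
| 0.4 SD | 41 / 40 / 37% | 55 / 69 / 89% |
| 0.6 SD | 79 / 83 / 89% | 88 / 96 / 99.8% |
| 0.8 SD | 97 / 99 / 99.7% | 98.6 / 99.9 / 100% |

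At ρ = 0 and 0.4 SD the two tests nearly agree (42% and 41%).

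**Step 4: unequal SDs.** Heating may widen the spread. If the SD during moxibustion is k times baseline, the SE ratio is √((1+k²)/(1+k²−2ρk)). At k = 3 this is √(10/8.2) = 1.10, √(10/7) = 1.20 and √(10/5.8) = 1.31. Power at 0.4 root-mean-square SD is then 42/41/40% against 49/55/63%. The loss is smaller but remains.

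**Step 5: the fallback.** If the unnamed non-parametric test were Mann-Whitney, type I error would be about 2.0/0.8/0.1%. Power at 0.4 SD would be 39/37/35%, against 53/68/88% for Wilcoxon signed-rank.

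**Step 6: number of tests.** During versus before and after versus before, at 4 sites in 2 sessions, is 2 × 4 × 2 = 16 tests. If these were independent and every null true, the chance of at least one result below 0.05 would be 1 − 0.95¹⁶ = 56%. Correlation between the tests changes this figure. Tests restored to an exact 5% level therefore need a multiplicity rule.

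**The case against.** The strongest reply is that the SAP sentence is generic. It lists no contrasts and nowhere says that before-versus-during or site-versus-site will be tested as independent samples. A competent analyst would pair, and research managers are to check the methods. It is true that the within-person contrasts are inferred from the design. But the sentence covers all numerical variables and offers no paired alternative. An analyst who pairs departs from the plan, and the check in Part 3, 1.1 has no stated standard to check against.

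A second reply is that the loss depends on assumed values. That stands: it is almost nil at 0.8 SD, absent at ρ = 0, and smaller when SDs differ. The mismatch between test and design does not depend on those values; only its size does.

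A third reply is that much of the study is unaffected. For COPD versus healthy control at a single site, the groups are independent and the named test is suitable.

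A reader might infer that the plan inflates false positives. The documents do not support that: it would need a negative within-person correlation, and they give none. A reader might also infer that comparing COPD with control on Heart-minus-Lung differences would settle site specificity. It would not. The groups are not described as randomised or matched, and their age criteria differ (35 to 75 years, against 20 or over).

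**Conclusion.** The concern holds and should be fixed before analysis. The only named test for numerical variables does not fit the contrasts on which the moxibustion part depends, nor the site contrasts within the other two groups.

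If the within-person correlation is positive (likely, but an assumption), the test is conservative. At 0.4 SD with equal SDs, the power lost is about 14, 30 and 52 percentage points at ρ = 0.3, 0.5 and 0.7 (55.0 − 40.9, 69.4 − 39.6 and 89.0 − 37.0). These figures rest on normal data, n = 40 with no dropout, and a two-sided 5% level; they illustrate size and do not predict this trial's loss. It would go too far to call the whole analysis invalid, because single-site COPD versus control comparisons are sound in this respect.

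**What to change.** In Part 3, 2.3:

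1. Keep the independent-sample t test (Mann-Whitney if non-normal) for between-group comparisons with one value per person. Add a COPD versus control comparison of each person's Heart-minus-Lung PU difference, separately for the wrist pair (HT7 minus LU9) and the elbow pair (HT3 minus LU5). State that the groups are not described as randomised or matched.
2. For within-person contrasts, reduce PU to one stated summary per person, site, period and session. Use a paired t test (Wilcoxon signed-rank if non-normal) for during or after versus before, and for site versus site within a group.
3. For treated versus untreated meridian and for Heart versus Lung session, use paired tests of changes from the 5-minute pre-moxibustion baseline. Analyse the unheated forearm midpoints separately from the heated point (HT3 or LU5), so that local heating is not read as a meridian effect. Note that session may be confounded with order, since section 2.6.3 describes no order randomisation.
4. Name a small set of primary contrasts, or apply an adjustment such as Holm.

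In Part 2, 2.5, give the statistician the participant, site, session and period identifiers, and limit the blinding claim to the COPD versus control codes.

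Cost: wording changes, a little more analysis work, and less power per contrast if Holm is used. No new data or procedures are needed. The statistician is no longer masked to the intervention group, but its sites, periods and sessions make it recognisable from the data anyway.

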2.1 Study design

This is a prospective and open-label clinical trial. The time frame of the trial ranges from July 2019 to December 2020. A total of 120 participants will be divided into the healthy control group, COPD group and healthy intervention group., with 40 in each group respectively.

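### SAP 2.3 defines no contrast for the site-specificity objective, and its only named test for numerical data does not fit the within-person comparisons in the moxibustion arm

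*Combined protocol and SAP*

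**What the plan says.** - **Objective** (Part 1, (2) Study objects): "This study aims to investigate the site specificity for the meridian-visceral association and surface-surface association between two specific meridians".
- **Groups** (Part 2, 2.1): healthy control, "COPD group and healthy intervention group., with 40 in each group respectively".
- **Control and COPD recordings** (2.6.3 (1)): "The probes will be left at 4 measuring acupoints", two on each meridian, in one 5-minute recording.
- **Moxibustion arm** (2.6.3 (2)): "Two sessions of moxibustion intervention will be performed in the Heart meridian and Lung meridian successively". In each session "the probes will detect the blood flow curve and PU in four sites in two meridians", and "The measuring time points include 5 minutes before moxibustion, 15 minutes during moxibustion and 5 minutes after stopping moxibustion".
- **Outcome** (Part 2, section 3): "Primary outcomes will be blood flow curve and blood perfusion units (PU) of relevant sites along the Heart and Lung meridians". No site, time window or summary measure is singled out.
- **Analysis** (Part 3, 2.3): "Independent sample T test and Chi-square test (χ^2 test) will be used for numerical variables and categorical variables, respectively". An unspecified non-parametric test replaces these when the distribution is not normal, and the threshold is P < 0.05. Nothing further is said about inference.

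The flow diagram is not reproduced in the text available, and nothing here relies on it.

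**The concern.** Specificity is a claim about a difference between effects. For the meridian-visceral part, the question is whether COPD shifts perfusion more at Lung than at Heart sites. For the surface-surface part, it is whether heating one meridian changes perfusion more along that meridian than along the other. The plan defines neither contrast.

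The two halves of the study then go wrong in different ways:

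- **Moxibustion arm.** Before, during and after, Heart and Lung sites, and the two sessions are all measured in the same people. An independent-samples test ignores the pairing. If a person's readings correlate positively, the standard error is too large and real differences of small to moderate size are missed.
- **COPD versus control.** These are different people, so the independent t-test is usable. Applied site by site, however, it gives four separate answers and no test of specificity. Nothing in the plan prevents a significant Lung result beside a non-significant Heart result from being read as specificity, and that pattern can arise when the effects are equal.

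**Working it through.** **1. The plan's own figure.** Part 2, 2.2 sets N = 120 without an effect size, SD or power, so it cannot be reproduced. For reference, 40 v 40 independent people give 80% power at (1.96 + 0.84) × √(2/40) = 0.63 SD.

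**2. Structure of the moxibustion arm.** 2 sessions × 4 sites × 3 periods = 24 values per person. Any two of these from the same person form a pair, so the arm offers no independent-groups comparison.

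**3. Independent versus paired test on 40 pairs.** With equal SDs s and correlation r, the independent test uses SE = s√(2/n). The correct SE is s√(2(1 − r)/n). The first exceeds the second by 1/√(1 − r), which is 1.20, 1.41, 1.83 and 2.24 at r = 0.3, 0.5, 0.7 and 0.8. The approximate true type I error of the independent test is 2[1 − Φ(1.96/√(1 − r))]. At r = 0.3 this is 2[1 − Φ(2.34)] = 1.9%, and at r = 0.5 it is 2[1 − Φ(2.77)] = 0.6%.

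The documents give no correlation, so r is assumed over a range. Independent-test figures are simulated and paired power is from the noncentral t, two-sided 0.05:

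| r | Type I error, independent | Power at 0.2 SD, ind. v paired | Power at 0.4 SD | Power at 0.6 SD |
|---|---|---|---|---|
| −0.3 | 8.6% | 18 v 12% | 43 v 33% | 73 v 63% |
| 0 | 5% | 14 v 14% | 42 v 41% | 76 v 74% |
| 0.3 | 2.0% | 10 v 18% | 41 v 55% | 79 v 88% |
| 0.5 | 0.6% | 7 v 23% | 39 v 69% | 83 v 96% |
| 0.7 | 0.1% | 3 v 36% | 37 v 89% | 89 v 100% |
| 0.8 | 0.0% | 1 v 50% | 35 v 97% | 92 v 100% |

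At 0.8 SD and r of 0.3 or more, both tests have 97% power or more.

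With unequal SDs the variance of the difference is s₁² + s₂² − 2r·s₁s₂ and the loss shrinks. Effects are in units of the root-mean-square SD, for r = 0.3/0.5/0.7/0.8:

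- SD ratio 2: type I error about 2.7/1.3/0.4/0.2%; power at 0.4 SD 42/41/39/38% v 52/62/75/83%.
- SD ratio 3: type I error about 3.3/2.2/1.2/0.9%; power at 0.4 SD 42/41/40/40% v 49/55/63/68%.

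**4. COPD versus control (illustration).** Simulated trials of 40 v 40 had two Lung and two Heart sites and the same true shift at all four. Correlations were 0.3 to 0.8 throughout, or 0.8 within and 0.3 or 0.5 between meridians. Three readings of Lung significant, Heart not were tried: any site, both sites, or the site average.

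| True shift at every site | Lung significant, Heart not | Direct Lung-minus-Heart test, same direction |
|---|---|---|
| 0.3 to 0.63 SD | about 5 to 20% | about 2.5% |
| 0.8 SD | about 1 to 8% | about 2.5% |
| 1.0 SD | 0.0 to 1.3% | about 2.5% |

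**5. What direct contrasts could detect** (80% power, noncentral t, equal SDs). The unit values are 0.634 SD for 40 v 40 and 0.454 SD of the difference for 40 pairs. Results are for r = 0.3/0.5/0.7/0.8.

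- COPD v control, one site per meridian: 0.634√(2(1 − r)) = 0.75/0.63/0.49/0.40 SD.
- COPD v control, two sites averaged: 0.634√(1 + r_within − 2r_between) = 0.53/0.45/0.35/0.28 SD if all correlations are equal, and 0.69 SD if r_within = 0.8 and r_between = 0.3.
- Moxibustion arm, double difference over two sessions with one site per meridian: 0.454√(4(1 − r))/2 = 0.38/0.32/0.25/0.20 SD of a change score, as the average stimulated-minus-other difference per session.

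**The case against.** **The sentence in SAP 2.3 is generic.** It does not assign the independent t-test to the moxibustion comparisons, and a competent statistician would pair the data. It is true that the wrong-test point rests on taking the sentence at its word. But Part 2, 2.5 gives the analysis to third-party statisticians who are blinded to the protocol, so Part 3 is what they have to work from. Part 3, 1.1 has research managers check the methods, but gives them no contrast to check against. Even with paired tests, the specificity contrast would still be undefined.

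**The loss depends on unknown quantities.** This stands. At zero correlation the two tests are equivalent. At −0.3 the named test is too liberal (8.6%). With a large effect, or with very unequal SDs and low correlation, little is lost.

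**Lost power is not the whole error picture.** This also stands. Change from baseline at 4 sites × 2 later periods × 2 sessions is 16 possible tests. If they were independent, the chance of at least one false positive would be 1 − 0.95^16 = 56%, or 1 − 0.98^16 = 28% at the deflated 2.0% per test. Multiplicity is a separate matter. The power statement here is per test.

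**The COPD illustration describes a reading that the plan does not announce.** Correct. It shows why a contrast is needed and does not describe a stated method. At 1.0 SD that reading errs less often than the direct contrast.

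**Scope.** Heart-versus-Lung comparisons inside the COPD or control group are also within-person, so the same gap applies there.

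**Conclusion.** The concern holds and should be fixed before analysis. A stated objective has no defined test, and the only test named for numerical variables does not suit any comparison inside one of the three arms. Neither conclusion depends on an assumed number.

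The size does depend on assumptions. Under positive within-person correlation the consequence in the moxibustion arm is lost power, not false positives. The loss at 0.4 SD runs from 7 percentage points (correlation 0.3, SD ratio 3) to 62 (correlation 0.8, equal SDs). For COPD versus control the defect is an omission: the site-by-site test is valid but does not answer the specificity question.

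**What to change.** Add to Part 3, 2.3:

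- **(a) Meridian-visceral.** Test the group-by-meridian interaction, for example an independent t-test of COPD versus healthy control on each person's Lung-minus-Heart PU difference. Report single-site comparisons as supporting.
- **(b) Surface-surface.** In the moxibustion arm, replace the independent test with a within-person one (paired test or mixed model) of stimulated meridian by measured meridian, on change from the 5-minute baseline. The sponsor should fix the sites and time window in advance, and leave the directly heated point out of the contrast or handle it separately. HT3 is heated in one session and LU5 in the other, so only the two forearm midpoints are unheated in both.
- **(c) Claims.** Base specificity claims on (a) and (b), not on comparing P values across sites.

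The sponsor should also say how the blood flow curve, named as a primary outcome, enters the analysis. The contrasts above cover PU only.

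**Cost.** Wording only: every site and period needed is already recorded. The statistical price is sensitivity. The figures in step 5 for (a) are a Lung shift in excess of the Heart shift. The 0.63 SD for a single site, or 0.51/0.55/0.58/0.60 SD for a two-site Lung average [0.634√((1 + r)/2)], is a plain Lung shift. The two are comparable only if Heart sites do not move. If Heart moves half as much as Lung, the Lung shift needed for (a) doubles, to 1.50/1.27/0.98/0.80 SD with one site per meridian or 1.06/0.90/0.69/0.57 SD with two averaged. With 40 per group set without a power calculation, the sponsor should know this before fixing the contrast.
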